3.4 STUDY CALENDAR

3.4.1 Study Calendar for Phase I

Procedure	Screening ¹	Baseline / Day 1 ²	Odd numbered Weeks (W1, W3, W5, W7 onwards) ³	EOT ⁴	Safety follow up ⁵	Long Term follow up ⁶
Treatment ³		X	X			
NIH Advance Directives Form ⁷		X				
Medical History ¹⁷	X					
Height	X					
Physical exam, weight, vital signs, ECOG ¹⁶	X	X	X	X	X	
Skin assessment ¹⁸		X	X	X	X	
HIV, HCV, HepB	X					
EKG	X			X	X	
CBC with differential	X	X	X	X	X	
Biochemical profile ⁸	X	X	X	X	X	
Tumor Markers ⁹		X	X	X		
CD4 ¹⁰	X					
TSH with reflex Free T3 and T4, lipase, amylase, CRP		X	X ¹¹			
Urinalysis	X					
Urine or serum pregnancy testing in women of childbearing potential	X	X	X			
PT, INR, PTT		X				
Tumor evaluation (CT Scan / MRI)	X	X	X ¹²			X
Brain CT/MRI ¹³	X					
Concomitant Medications		X	X	X	X	
Adverse events		X	X	X	X	
Biopsy for immune analysis ¹⁴		X	X			
Research Blood ¹⁵		X	X	X		
Telephone Follow Up					X	X

1. Screening evaluations performed within 28 days prior to the first drug administration, unless specified in Section **2.2**.

2. Baseline evaluations performed within 2 weeks prior to first drug administration.

Note: Baseline Labs will not be redrawn if done already as screening within the 2 weeks prior to drug administration.

3. Treatment:

- Trial treatment will be given with either HPV vaccine monotherapy (Arm 1A) or the combination of HPV vaccine + M7824 (Arm 1B) for a year.
- HPV vaccine will be given on D1, D15 and D29 followed by every 4 weeks thereafter and M7824 will be given every 2 weeks.
- Both of these agents may be discontinued early for unacceptable toxicity or disease progression. Treatment beyond a year may be given per PI discretion.
- Administration of study agents and indicated evaluations can be done up to 14 days earlier or delayed up to 14 days due to holidays, inclement weather, conflicts, or similar reasons.

The timing of subsequent administrations is adjusted to maintain a minimum of 11 days between treatments of similar agents.

4. EOT – End of treatment visit: Where feasible, on the day of or within 7 days of the decision to discontinue treatment prematurely before completion of one year of treatment.

5. Approximately 28 days (+/- 7 days) after last treatment. If subjects are not willing to come to NIH for FU visit, they will be contacted by phone to assess adverse events and for such participants no labs will be needed at FU.

6. Participants who have come off treatment for disease progression will be followed by phone annually for survival. Participants who have not progressed on treatment will continue to be followed and scanned per investigator discretion until progression. Initial and follow up courses of treatment may extend beyond a year per investigator discretion.

7. As indicated in Section **12.3**, all subjects will be offered the opportunity to complete an NIH advanced directive form. This should be done preferably at baseline but can be done at any time during the study as long as the capacity to do so is retained. The completion of the form is strongly recommended, but is not required.

8. Biochemical profile: Acute care, hepatic and mineral panel as described in Sections **2.2** and **2.4**.

9. Evaluate CEA, CA19-9, CA125 and CA15-3 at baseline and follow elevated values thereafter (for participants enrolled on the phase I portion of the protocol).

10. In HIV positive participants.

11. Every 8 weeks for participants.

12. Imaging will be performed every 8 weeks. In the event of a PR or CR tumor imaging assessments may be performed every 3 months (+/- 2 weeks) at the discretion of the investigator. Tumor assessment should be continued beyond end of treatment in participants who have not experienced PD until they experience PD in order to assess PFS. MRI (with gadolinium) will be used when CT scan is not an option to follow the disease. Bone scans and other imaging assessments may also be performed as clinically indicated.

13. In participants with known CNS disease as described in Section 2.1.2.3; MRIs may be performed as clinically indicated in this population.

14. Where feasible, optional biopsies may be done at baseline and at week 9 and will likely be CT guided. If a recent (\leq 6 months preferred) outside biopsy has been performed that specimen may be used in lieu of a baseline biopsy for both phase I and II participants.

15. Where feasible, research blood (see Section 5.1) will be collected at the following time points:

- PKs and ADAs – performed only on Arm 1B (bintralusp alfa plus vaccine)
 - Samples for PK analysis will be taken prior to infusion and following infusion on W1 and W5 and prior to infusion on W3 and W11 or with end of treatment labs if patients comes off treatment prior to any of those timepoints; and
 - Samples for ADA analysis will be taken prior to infusion on W1, W5, and W11 or with end of treatment labs if participants come off treatment prior to any of those timepoints.
- Samples for AVA analysis will be taken prior to infusion on W1, W3, W5, W11, and restaging visits or with end of treatment labs if participants come off treatment prior to any of those timepoints.
- All other blood samples
 - Baseline, Week 3, and Week 5; restaging visits per PI discretion.
- Note: Samples may be sent to Precigen, Inc for additional analyses (see Section **5.1.9**).

16. Vital signs at screening should include pulse oximetry on room air.

17. Medical history will include monitoring for signs of bleeding.

18. Skin assessment must be performed at baseline and at least every 6 weeks, starting on week 5 during treatment and at the end of treatment or at the 28 (± 7 days) day safety follow-up (if not performed in the previous 6 weeks).

3.4.2 Study Calendar for Phase II

Procedure	Screening ¹	Baseline ²	Week 1	Week 3	Week 4-5 ¹⁸	EOT ⁴	Safety follow up ⁵	Long Term follow up ⁶
Biochemical profile ⁸	X	X	X	X	X	X	X	
CD4 ⁹	X							
TSH with reflex Free T3 and T4, lipase, amylase, CRP		X	X	X	X			
Urinalysis	X							
Urine or serum pregnancy testing in women of childbearing potential	X	X	X	X				
HLA typing ¹⁷		X						
PT, INR, PTT		X						
Tumor evaluation (CT Scan / MRI) ¹⁰	X	X			X			
Concomitant Medications		X	X	X	X	X	X	
Adverse events		X	X	X	X	X	X	
Biopsy for immune analysis ¹¹		X			X			
Research Blood ¹²		X	X	X	X	X		
Saliva sample ¹⁵		X	X	X	X	X	X	
Taken off treatment for definitive treatment ¹⁹					X			
Telephone/email Follow Up							X	X

1. Screening evaluations performed within 28 days prior to the first drug administration, unless specified in Section [2.2](#).

2. Baseline evaluations performed within 2 weeks prior to first drug administration.

Note: Baseline Labs will not be redrawn if done already as screening within the 2 weeks prior to drug administration.

Note: Imaging within 4 weeks prior to drug administration.

3. Therapeutic agents administered will be as outlined in Section [3.1](#):

- Participants will be planned to receive two doses of treatment (HPV vaccine alone in Arm 2A) before definitive standard of care therapy.
- Administration of study agents and indicated evaluations can be done up to 3 days earlier or delayed up to 3 days due to holidays, inclement weather, conflicts, or similar reasons.

The timing of subsequent administrations is adjusted to maintain a minimum of 11 days between treatments of similar agents.

4. EOT – End of treatment visit: Where feasible, on the day of or within 7 days of the decision to discontinue treatment prematurely before completion of one year of treatment prematurely or one month of neoadjuvant or induction treatment. Note: Does not need to be completed if drug is withheld after these timepoints and such participants will be considered off-treatment.

5. Approximately 28 days (+/- 7 days) after last treatment. If subjects are not willing to come to NIH for FU visit, they will be contacted by phone to assess adverse events and for such participants no labs will be needed at FU.

6. Participants who have completed neoadjuvant or induction immunotherapy on the phase II portion of the protocol will be followed by phone or email for recurrence, adverse events and survival starting 2 months (+/- 2 weeks) after safety visit and then annually (+/- 1 month) until the patient is 5 years out from surgery or completion of chemoradiotherapy.

7. As indicated in Section **12.3**, all subjects will be offered the opportunity to complete an NIH advanced directive form. This should be done preferably at baseline but can be done at any time during the study as long as the capacity to do so is retained. The completion of the form is strongly recommended but is not required.

8. Biochemical profile: Acute care, hepatic and mineral panel as described in Sections **2.2** and **2.4**.

9. In HIV positive participants.

10. Imaging (CT of neck and chest/ MRI, if indicated, for oropharyngeal cancer participants; CT of skull, neck and chest/ MRI, if indicated, for sinonasal SCC; no CT chest required if PET/CT available) at baseline/screening, and at Week 4-5 (CT of neck/ MRI, if indicated, for oropharyngeal cancer participants; CT of skull, neck/ MRI, if indicated, for sinonasal SCC). MRI (with gadolinium) will be used when CT scan is not an option to follow the disease. Bone scans and other imaging assessments may also be performed as clinically indicated. Post-treatment imaging is to be strongly pursued but is not required and may be waived at the discretion of the PI.

11. Where feasible, biopsies will be done at baseline as well as at week 4-5. Biopsies will be done by ENT under direct visualization. Where feasible at least 2 cores will be obtained. If a recent (\leq 6 months preferred) outside biopsy has been performed that specimen may be used in lieu of a baseline biopsy. For patients that have surgery as definitive treatment, Week 4-5 biopsy may be omitted: in this case tumor biospecimens will be obtained from the institution where the patient underwent surgery after the patient signs that institution's release document.

12. Where feasible, research blood (see Section **5.1**) will be collected at baseline, week 3 and week 45 with the following exceptions:

- Samples for AVA analysis will be taken prior to infusion on W1, W3, with research labs on 4-5 or with end of treatment labs if participants come off treatment prior to any of those timepoints.
- Note: Samples may be sent to Precigen, Inc for additional analyses (see Section **5.1.9**).

13. Vital signs at screening should include pulse oximetry on room air.

14. Medical history will include monitoring for signs of bleeding.

15. Only for p16+ oropharyngeal cancer patients: Collection of saliva by mouth rinse and gargle with 15-20 mL 0.9% NaCl for 30 seconds and spitting into the collection tube. Where possible, saliva samples will be analyzed for HPV DNA detection and quantification.

16. Skin assessment must be performed at baseline and at least every 6 weeks starting on week 5 during treatment and at the end of treatment or at the 28 (\pm 7 days) day safety follow-up (if not performed in the previous 6 weeks).

Abbreviated Title: *Combo Immunotx in HPV OPSCC*

Version Date: 09.20.2023

17. HLA A, B, C and DR, DQ and NGS A, B, C and DR, DQ, at any time prior to treatment start. Patients who have had HLA typing previously performed at NIH do not require retesting.
18. Preferably scheduled for Week 5, with Week 4 an option to not interfere with activities required for arrangements for definitive treatment. An earlier timepoint may also be used to avoid interfering with definitive treatment, but should be at least a day after the second vaccination.
19. Upon completion of induction or neoadjuvant immunotherapy participants on the phase II portion of the protocol will be taken off treatment and referred back to their home institutions for definitive standard of care therapy and follow up will be performed per superscript # 6 above.

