3.3.3 Study Accrual Halting Rules

Accrual will be halted if:

- Phase 1 and Phase 2:
 - There is an occurrence of any death (other than death related to progressive disease or accidental death) that occurs within 30 days of administration of study agents (PRGN-2009 and M7824) for both Phase 1 and Phase 2.
- Phase 2 only:
 - There is a delay in initiation of definitive standard of care therapy of 4 weeks or more beyond the planned start date due to treatment-related toxicities from HPV vaccine in two participants.

- There is occurrence of treatment-related ADRs from HPV vaccine of either Grade 4 (except for laboratory values that are asymptomatic or resolve to Grade ≤ 1 or baseline within 7 days) or of Grade 3 not resolving to Grade ≤ 1 or baseline within 7 days in two participants.

The IRB and the sponsor will be notified if one of the study accrual halting rules has been reached.

The accrual halt will be lifted once the data has been reviewed and there has been a reassessment of available safety information prior to reopening the study to accrual and allowing the study to proceed.

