3.6 CRITERIA FOR REMOVAL FROM PROTOCOL THERAPY AND OFF STUDY CRITERIA

Regardless of reason for removal from study therapy, participants will be asked to have a 28 day follow up safety visit. Participants who are unable or unwilling to return for this visit will be asked to review any safety concerns by phone within this time period.

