6 DATA COLLECTION AND EVALUATION

6.1 DATA COLLECTION

The PI will be responsible for overseeing entry of data into a 21 CFR Part 11-compliant data capture system provided by the NCI CCR and ensuring data accuracy, consistency and timeliness. The principal investigator, associate investigators/research nurses and/or a contracted data manager will assist with the data management efforts. Primary and final analyzed data will have identifiers so that research data can be attributed to an individual human subject participant.

All adverse events, including clinically significant abnormal findings on laboratory evaluations, regardless of severity, will be followed until return to baseline or stabilization of event. Document AEs from the first study treatment, study day 1, through 28 days after the subject received the last product administration. After 28 days, only adverse events which are serious and related to the study investigational agent need to be recorded. For participants enrolled on the phase II portion of the protocol adverse events which occur while participant is being treated with standard chemoradiation and which are not attributed to immunotherapy need not be captured.

An abnormal laboratory value will be recorded in the database as an AE **only** if the laboratory abnormality is characterized by any of the following:

- Results in discontinuation from the study;
- Is associated with clinical signs or symptoms;
- Requires treatment or any other therapeutic intervention;
- Is associated with death or another serious adverse event, including hospitalization;
- Is judged by the Investigator to be of significant clinical impact; and/or
- If any abnormal laboratory result is considered clinically significant, the investigator will provide details about the action taken with respect to the test drug and about the participant's outcome.

End of study procedures: Data will be stored according to HHS, FDA regulations, and NIH Intramural Records Retention Schedule as applicable.

Loss or destruction of data: Should we become aware that a major breach in our plan to protect subject confidentiality and trial data has occurred, this will be reported expeditiously per requirements in Section [7.2.1](#).

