7.3 NCI CLINICAL DIRECTOR REPORTING

Problems expeditiously reviewed by the OHSRP in the NIH eIRB system will also be reported to the NCI Clinical Director/designee; therefore, a separate submission for these reports is not necessary.

In addition to those reports, all deaths that occur within 30 days after receiving a research intervention should be reported via email unless they are due to progressive disease.

To report these deaths, please send an email describing the circumstances of the death to [contact] within one business day of learning of the death.

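### A safety contact held before day 28 leaves the end of the AE recording period with no scheduled enquiry, most clearly in Phase I; moving the early edge of the window or adding a phone check closes the gap

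*Combined protocol and SAP*

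**What the plan says.** Four parts of the protocol bear on the weeks after the last dose.

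- **Contact.** Section 3.4.2 (Phase II calendar), note 5, sets the safety follow-up at "Approximately 28 days (+/- 7 days) after last treatment". Note 5 of section 3.4.1 (Phase I) has the same timing. Both allow a phone call without labs when the participant will not travel. Section 3.6 gives no tolerance: "participants will be asked to have a 28 day follow up safety visit".
- **AE recording.** Section 6.1: "Document AEs from the first study treatment, study day 1, through 28 days after the subject received the last product administration". From then on the duty narrows: "After 28 days, only adverse events which are serious and related to the study investigational agent need to be recorded".
- **Deaths.** Section 3.3.3 halts accrual for a death, other than from progression or accident, "that occurs within 30 days of administration of study agents (PRGN-2009 and M7824) for both Phase 1 and Phase 2". Section 7.3 adds a reporting duty: "all deaths that occur within 30 days after receiving a research intervention should be reported via email unless they are due to progressive disease".
- **Next contact.** In Phase II (3.4.2, note 6) a phone or email contact about recurrence, AEs and survival is due 2 months (+/- 2 weeks) after the safety visit. In Phase I (3.4.1, note 6) participants who stopped for progression are phoned once a year about survival; the others are followed and scanned at the investigator's discretion.

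**The concern.** The contact is the last scheduled enquiry about AEs tied to the end of treatment, yet its window opens a week before the AE recording period closes. A site that calls on day 21 follows the calendar and has no scheduled occasion to ask about days 22 to 28.

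Two things are at stake. One is completeness of AE data, above all for new events that are not both serious and related, since those need not be recorded after day 28 and nothing later would prompt for them in Phase I. The other is how soon the study team learns of a death that should halt accrual. In Phase II participants return to their home institutions for definitive therapy (section 3.1), so informal awareness cannot be relied on. The reporting clock in section 7.3 starts only when the team learns of the death.

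**Working it through.** The plan gives no figure of its own to reproduce here. The check is day arithmetic on its stated windows, counting days from the last dose and taking a contact on day *d* to cover events up to day *d*.

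**Inputs.** Contact window 28 +/- 7 days (3.4.1 and 3.4.2, note 5); AE period to day 28 (6.1); death window to day 30 (3.3.3).

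**Permitted contact days.** 28 − 7 = 21 to 28 + 7 = 35, which is 15 days.

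**Days left without a scheduled contact.** AE gap = max(0, 28 − d); death gap = max(0, 30 − d).

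| Contact day | AE gap | Death gap |
|---|---|---|
| 21 | 7 (days 22–28) | 9 (days 22–30) |
| 28 | 0 | 2 (days 29–30) |
| 30 | 0 | 0 |
| 35 | 0 | 0 |

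Of the 15 permitted days, 7 (days 21–27) leave an AE gap and 9 (days 21–29) leave a death gap. These are counts of days, not probabilities; the documents do not say how often contacts are held early.

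**What causes the death gap.** At day 21 it splits as 9 = (28 − 21) + (30 − 28) = 7 + 2. The tolerance accounts for 7 days. The other 2 come from a nominal visit at day 28 set against a death window of 30 days.

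**When the gap is next looked at, Phase II.** Taking 2 months as 61 days, the contact after a day-21 visit falls between 21 + 61 − 14 = day 68 and 21 + 61 + 14 = day 96, nominally 21 + 61 = day 82. The delay runs from 68 − 30 = 38 days to 96 − 22 = 74 days, about 5 to 11 weeks. Note 6 lists AEs among the topics, but the calendar grid has no AE mark under long-term follow-up.

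**When the gap is next looked at, Phase I.** After progression, the next fixed contact is the annual survival call, so a death may be learned of up to about a year late. Without progression, no date is fixed. The grid has no AE mark under long-term follow-up in either case.

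**The case against.** The strongest reply is that a visit tolerance is not a cut-off for data. Section 6.1 imposes recording to day 28 independently of when the visit takes place, section 3.6 describes the visit as a 28-day one, and a site that goes early still owes the remaining days. Serious related events have no end date in 6.1. SAE and death reports run from awareness (8.3, 7.3), so they need not wait for a visit.

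This stands as far as it goes. A reader might infer that a day-21 contact ends ascertainment and that later events go unobserved. The documents do not support that: the duty continues, Phase II has a later contact whose note names AEs and survival, and Phase I progressors have the survival call. For deaths the problem is delay, not loss. But a duty without a scheduled enquiry depends on someone volunteering the information, and for AEs in Phase I no later fixed contact makes up for it.

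Other limits also stand:

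- A delay of up to a year applies only to Phase I participants who stopped for progression, not to Phase I as a whole. The halting rule itself excludes deaths from progression or accident.
- A 28-day AE period and a 30-day death rule serve different purposes and do not contradict each other.
- Section 6.1 exempts Phase II AEs arising during standard chemoradiation and not attributed to immunotherapy, so some late events are not required data.
- Table 8 in section 14.1.2 already shows 3 + 3 + 11 + 22 = 39 treated, against an accrual ceiling of 50 (10.2). Accrual appears largely complete, which limits what a faster halt could protect.
- DLTs are counted over 28 days from the start of therapy (3.1.1), so the DLT assessment is untouched.

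**Conclusion.** The point holds as a cheap improvement to safety ascertainment. A compliant contact before day 28 leaves up to 7 days of the AE period with no scheduled enquiry. In Phase II those days are next asked about roughly 5 to 11 weeks later, by recall; in Phase I no later AE contact is scheduled. Deaths on days 22 to 30 may become known late rather than be missed, and days 29 and 30 are uncovered even by a visit on day 28.

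The 7 and 9 days are the worst permitted case. A contact on day 28 or later has no AE gap, and one on day 30 or later has neither gap. The conclusion assumes that no unscheduled contact happens to fill the interval. How many participants are affected cannot be derived from the documents.

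**What to change.** In note 5 of both calendars, take one of two routes:

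1. Remove the early side of the window so that the contact cannot precede the end of the AE period, for example day 28, +7 days. This reduces the AE gap to zero and leaves at most 2 days of the death window.
2. Keep the present window, but when the visit falls early add a brief phone check of AEs and vital status on or after day 30. This closes both gaps.

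Align section 3.6 with whichever is chosen, and reconcile the Phase II grid with note 6 on whether AEs are asked about in long-term follow-up. Leave the halting rule in 3.3.3 as it is.

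The cost is calendar wording and, under the second route, a short call. The earliest contacts move by 28 − 21 = 7 days, or 30 − 21 = 9 days for a check at day 30. In Phase II, with a last vaccination on study day 15, the earliest visit moves from study day 36 (15 + 21) to 43 (15 + 28). It may then overlap the start of definitive therapy, where attribution is harder. The phone check largely avoids this, because the visit itself can stay early.
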